Exclusion criteria	
1) Pregnant or lactating women;
 
(2) Chronic cardiac dysfunction, pulmonary hypertension and/or right ventricular enlargement caused by chronic cardiopulmonary disease, cardiogenic shock or after major cardiac surgery before ARDS;
 
3) right ventricular myocardial infarction;
 
4) Uncorrected hypotension, hypoxemia and hypercapnia, or acid-base balance disturbance
 
5) Mechanical ventilation driving pressure <math>\geq 18\text{cmH}_2\text{O}</math> before randomization
 
6) Rapid arrhythmia;
 
7) pericardial tamponade;
 
8) Pulmonary embolism;
 
9) severe renal insufficiency;
 
10) severe liver insufficiency;
 
11) Failure to sign informed consent;
 
12) known allergy to the test drug;
 
13) Patients who have participated in other clinical trials within 30 days

Intervention	Patients will be randomized to treatment group A: intravenously injected levosimendan 12.5mg with 5% glucose injection 50ml configuration at 2ml/h for 24h, or treatment group B: control group with 5% glucose injection 2ml/h for 24h.

Evaluation criteria: Primary endpoint: Secondary end point: Safety evaluation	Primary endpoint: The rate of RVD occurrence within 48 hours after randomization. secondary end points: 1) Changes in the following indexes were assessed 48h after random administration including : TAPSE, S ', RV FAC, RVEDA/LVEDA PVR, RV-PA coupling, CI, SVI, SVR, ScvO2 SOFA scoring 2) Mortality at 28 days after randomization and in hospital
Statistical Methods:	Sample size: 23 cases in the experimental group and 23 cases in the control group. Considering the 20% shedding rate, the statistical sample size was 29 cases in the experimental group and 29 cases in the control group, and a total of 58 subjects were enrolled.  Primary endpoints: incidence of RVD 48h after randomization  Safety endpoints:  Safety endpoints are those where subjects have severe adverse reactions related to the drug that are persistent and cannot be corrected according to the protocol
Study duration	2023.02-2025.12
Subject attendance time	From the time subjects were recruited to the time each subject completed all follow-up visits
Research unit/location	Wuhan Union Medical College Hospital, the First Affiliated Hospital of Zhengzhou University, Henan Provincial People's Hospital
Name, qualifications and contact information of the principal investigator	
	[name], [contact], has obtained the GCP Certificate

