## **2. Study objective/end point**

The main objective is to (confirm) about whether or not the leosimendan improve mechanical ventilation in patients with ARDS right heart function.

secondary objective is to exploratory whether or not levosimendan reduces mechanical ventilation in patients with ARDS mortality

Primary endpoint: the incidence of RVD after 48h ending of randomization

Secondary endpoint: (1): TAPSE, S ', FAC, RVEDA/LVEDA PVR, RV-PA coupled CI, SVI, SVR, ScvO2 SOFA score after 48h ending of randomization. (2) 28-day mortality rate, in-hospital mortality rate.

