## **3. Research design**

### **3.1 Overall Design**

Prospective, multicenter, randomized controlled study. According to the random allocation method, the subjects were divided into experimental group and control group; The control group was injected with 50ml 5% glucose for 24h, and the experimental group was injected with 12.5mg levosimendan for 24h according to the experimental protocol. Right ventricular function was compared between the two groups before and 48h after medication: Right ventricular area change fraction (RV FAC), tricuspid annulus systolic displacement (TAPSE), tricuspid annulus systolic S 'velocity (S'), right ventricular end-diastolic area/left ventricular end-diastolic area (RVEDA/LVEDA), pulmonary circulation resistance (PVR), right ventricular - pulmonary artery coupling (RV-PA), heart index (CI), Per Bo index (SVI), systemic

resistance (SVR), central venous oxygen saturation (ScvO2). SOFA score of patients with mechanical ventilation ARDS treated with levosimendan 48h after medication was evaluated, mortality rate at random 28 days, and all-cause in-hospital mortality.

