#### **4.4 Grouping method of subjects**

Patients will be randomized to treatment group A: intravenously injected levosimendan 12.5mg with 5% glucose injection 50ml configuration at 2ml/h for 24h, or treatment group B: control group with 5% glucose injection 2ml/h for 24h.

The randomization method of the experiment was block randomization and stratification according to the center. The statistical specialty used SAS 9.4 software to generate the blind base of the treatment group randomized according to the 1:1 allocation ratio between the experimental group and the control group. According to the enrollment sequence of patients, random numbers were issued from small to large and groups were assigned. The random number is reproducible, and the set parameters such as the number of centers, section length and seed number are recorded in the blind base.

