## 6. Research steps

- (1) Patients eligible for inclusion in the study were screened and informed consent was signed.
- (2) Patients were randomly assigned to the experimental group or the control group. Vital signs and hemodynamic parameters were recorded 1 hour before administration, and related indexes such as cardiac function and pulmonary circulation were detected by transesophageal ultrasound, as well as arterial blood gas, central vein blood gas, blood routine, liver and kidney function, electrolyte, myocardial enzyme profile and BNP were detected by blood sampling.
- (3) According to the study protocol, all subjects in the two groups began administration at 8am, and 8am vital signs, arterial blood gas, central vein blood gas,

blood routine, liver and kidney function, electrolytes, myocardial enzyme profile and BNP during medication period and the first 24 hours after medication completion were recorded. The related indexes of cardiac function, pulmonary circulation and hemodynamics were monitored by transesophageal ultrasound. Study withdrawal/early termination: Family members refuse to continue treatment if: Family members withdraw from the study; In the presence of experimental-related serious adverse reactions.

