## **7 Evaluation**

### **7.1 Primary and Secondary Endpoints/Outcome Evaluation Primary outcome:**

Rate of RVD at 48h randomized administration. Secondary outcome: 48h after random administration, the following indicators were assessed. Other indicators of right cardiac function were: TAPSE, S', FAC, RVEDA/LVEDA PVR RV-PA coupling CI, SVI, SVR, ScvO2 SOFA score after random 28-day mortality, in-hospital mortality

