## **9. Statistical analysis and statistical methods**

- (1) Case enrollment analysis: The total number of enrolled and completed cases in each center was listed, and three analytical data sets (FAS, PPS, SS) were determined. List the cases of shedding and elimination and their causes.
- (2) Demographic data and baseline analysis: descriptive demographic data and other baseline characteristic values; The number of cases, mean value, standard deviation, median, minimum value and maximum value of measurement data were calculated. Count and grade data calculation frequency and component ratio.
- (3) Effect analysis: CMH- $\chi^2$  test considering central effect was used for comparison between groups. t test or Wilcoxon rank sum test were used to compare the measures between groups.  $\chi^2$  test or Fisher's exact probability method were used to compare the classification indexes between groups. Rank data were obtained by Wilcoxon rank sum test or CMH- $\chi^2$  test. Survival data will be described using Kaplan-Meier curves and life tables. A nonparametric confidence interval for the median lifetime is calculated. Linear rank tests (logrank test and Wilcoxon test) were used to compare

survival between the treatment group and the control group. The Cox risk model was used to analyze the potential influence of covariates (predictors). Multivariate logistic regression was used to analyze dichotomous outcomes, such as recurrence rates, and this multivariate model would identify the most significant predictors. Logical or proportional advantage models will be used to adjust for prognostic factors. Precise confidence intervals will be calculated for the binary event incidence.

(4) Safety analysis: the incidence of adverse reactions was calculated; The sub-system lists the frequency and frequency of adverse reactions and calculates the percentage; A detailed list of adverse event cases; A detailed list of adverse event cases; The number and rate of "abnormal normal conversion" or "abnormal intensification" of laboratory indicators, electrocardiogram and physical examination after the test; List laboratory indicators, electrocardiograms, abnormal cases of physical examination and clinical explanations.

(5) Statistical software and general requirements use SAS software for analysis. All statistical tests were two-sided, and  $P \leq 0.05$  would be considered statistically significant.

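### The ten continuous 48 h secondary endpoints are compared without their pre-dose value or centre, and the protocol does not settle whether the outcome is the change or the 48 h value

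*Protocol*

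**What the plan says.** Protocol section 9(3) gives the method for continuous outcomes: "t test or Wilcoxon rank sum test were used to compare the measures between groups". Elsewhere in section 9(3), centre enters only through the CMH chi-square test. The covariate models it names are Cox, logistic and what appear to be proportional-odds models, and none of these is for a continuous outcome.

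Both covariates are available:

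- **Pre-dose values.** Section 6(2) says "Vital signs and hemodynamic parameters were recorded 1 hour before administration" and that "related indexes such as cardiac function and pulmonary circulation were detected by transesophageal ultrasound". It also lists a central venous blood gas at that time.
- **Centre.** Section 4.4 says "The randomization method of the experiment was block randomization and stratification according to the center". The project abstract names three centres.

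The form of the endpoints varies:

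- Project abstract: "Changes in the following indexes were assessed 48h after random administration", so a change.
- Section 2: a list of indices ending in "SOFA score after 48h ending of randomization", with no mention of change.
- Section 7.1: "48h after random administration, the following indicators were assessed", again with no mention of change.
- Section 3.1: "Right ventricular function was compared between the two groups before and 48h after medication", which could mean a comparison of changes or two separate comparisons.

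**The concern.** The endpoints concerned are TAPSE, S', RV FAC, RVEDA/LVEDA, PVR, RV-PA coupling, CI, SVI, SVR and ScvO2. They bear directly on the main objective, right heart function, in a trial planned around 46 evaluable patients. When the pre-dose value predicts the 48 h value, a test that ignores it leaves explainable variation in the error term. Ignoring a stratification factor can do the same if centres differ.

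The unsettled form is a second, linked problem. Under an unadjusted test, the change and the 48 h value give different estimates and different power in the same data. If the form is chosen once the data are visible, ten endpoints are open to selection. ANCOVA closes most of that gap, because with the baseline in the model the treatment estimate is the same whether the outcome is the 48 h value or the change.

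**Working it through.** **Inputs from the protocol.** Section 3.2: difference 20%, SD 20% (1.0 SD), two-sided alpha 0.05, power 0.9, 1:1 allocation, 23 evaluable per arm, 20% dropout, 29 per arm enrolled. Project abstract: three centres.

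**Assumptions, none documented.** Baseline-to-48 h correlation r = 0.3, 0.5, 0.7, with r = 0 as the worst case. Ratio k = baseline SD / 48 h SD = 1, 0.7, 0.5. Effect 0.7 SD, alongside the 1.0 SD implied by section 3.2, which that section does not tie to any of these indices. Entry requires right ventricular dysfunction (section 4.2), which may narrow the baseline range and lower both k and r.

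**Reproducing the plan's figure.** A two-sample t test at 1.0 SD has power 0.8997 with 22 per arm and 0.9125 with 23, so 23 is right. Then 23 / (1 − 0.2) = 28.75, rounded up to 29 per arm, 58 in total.

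**Variance against a t test on 48 h values.** Ratio = 1 − r².

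- r = 0.3: 1 − 0.09 = 0.91
- r = 0.5: 1 − 0.25 = 0.75
- r = 0.7: 1 − 0.49 = 0.51

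At r = 0.5 and 0.7 this is the precision of 23 / 0.75 ≈ 31 and 23 / 0.51 ≈ 45 patients per arm.

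**Variance against a t test on changes.** Ratio = (1 − r²) / (1 + k² − 2rk). The denominator equals (1 − r²) + (k − r)², so the ratio never exceeds 1 and equals 1 only when k = r.

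| | r = 0.3 | r = 0.5 | r = 0.7 |
|---|---|---|---|
| k = 1 | 0.65 | 0.75 | 0.85 |
| k = 0.7 | 0.85 | 0.95 | 1.00 |
| k = 0.5 | 0.96 | 1.00 | 0.93 |

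**Power, noncentral t, 23 per arm.** The t test has 46 − 2 = 44 error df. ANCOVA has 46 − 5 = 41 (intercept, treatment, baseline, two centre terms).

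| Effect | t test, 48 h value | ANCOVA r = 0 | r = 0.3 | r = 0.5 | r = 0.7 |
|---|---|---|---|---|---|
| 0.7 SD | 0.641 | 0.640 | 0.681 | 0.763 | 0.901 |
| 1.0 SD | 0.912 | 0.912 | 0.935 | 0.969 | 0.996 |

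**Simulation.** 10,000 trials per setting, 46 patients in centres of 16, 16 and 14, balanced within centre, normal data, no centre effect. Power at 0.7 SD:

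| | r = 0.3 | r = 0.5 | r = 0.7 |
|---|---|---|---|
| ANCOVA, k = 1 | 0.663 | 0.755 | 0.894 |
| Changes, k = 1 | 0.495 | 0.646 | 0.850 |
| ANCOVA, k = 0.7 | 0.665 | 0.758 | 0.896 |
| Changes, k = 0.7 | 0.612 | 0.745 | 0.905 |
| ANCOVA, k = 0.5 | 0.671 | 0.754 | 0.896 |
| Changes, k = 0.5 | 0.660 | 0.765 | 0.879 |

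For k = 0.5 to 0.7, ANCOVA is therefore between about one point below and five points above the test on changes. With an assumed between-centre SD of 0.3, the 48 h t test falls to about 0.61–0.62, and ANCOVA gives 0.671, 0.753 and 0.892. Type I error was 0.044–0.053 for all three methods. The simulated 95% CI half-width, in 48 h SD units, was 0.594 for the t test and 0.603, 0.575, 0.522 and 0.430 for ANCOVA at r = 0, 0.3, 0.5 and 0.7.

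**The case against.** **The test is valid, and covariates belong in a SAP.** A t or rank-sum test in a randomised trial is not wrong, these are secondary endpoints, and section 11.5.1 foresees a separate statistical analysis proposal. Validity is granted. But section 9(3) is not silent: it names an unadjusted test, and the protocol itself words the endpoint form in different ways. A later document would have to override this text.

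**Read as changes, the test already uses the baseline.** This stands in part. On the abstract's wording the pre-dose value is used, the comparison with 48 h values does not apply, and the remaining gain may be negligible, particularly if selection on right ventricular dysfunction lowers k. Centre is still unused, and a change score can also lose power: 0.495 against 0.641 at k = 1, r = 0.3.

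**The inconsistency is loose shorthand.** Sections 2 and 7.1 do not explicitly exclude change, so the passages can be read together. They do not have to be, and no passage settles it.

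**Dropping the rank-sum test has a cost for skewed indices.** Correct for strong skewness left untransformed. In a simulation with lognormal data, the same 46-patient layout and a 0.7 SD shift on the log scale, ANCOVA on the raw scale with a log-scale SD of 0.8 had power 0.52, 0.54 and 0.60 at r = 0, 0.3 and 0.5, against about 0.61–0.62 for rank-sum. On the log scale ANCOVA had 0.64–0.76. At log-scale SDs of 0.3–0.5, raw-scale ANCOVA roughly matched or beat rank-sum once r was at least 0.3. The transformed indices must therefore be chosen with care and in advance.

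**SOFA is in the same list.** It is left out here because section 6(2) lists no pre-dose SOFA score. Its own form is still worth stating.

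**Conclusion.** The point holds as an improvement that should be made, not as an error that invalidates the analysis. There is no bias and no type I error inflation. Against a t test on 48 h values, ANCOVA cuts the variance by 9%, 25% and 49% at r = 0.3, 0.5 and 0.7. Power at 0.7 SD rises from 64% to about 66–68%, 76% and 89–90%; at 1.0 SD it rises from 91% to about 93%, 96–97% and 99.6%. Against a t test on changes, the gain runs from nil to a 35% cut in variance, depending on k and r. At r = 0 nothing is gained.

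These sizes rest on assumed values of r, k and the effect, and on roughly normal data after any transformation, so confidence in the magnitude is moderate. The need to fix one endpoint form before analysis does not depend on those assumptions.

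**What to change.** 1. In section 9(3), for the ten right-heart and haemodynamic indices only, replace the t or rank-sum test by ANCOVA of the 48 h value on treatment, the index's own pre-dose value and centre. Report the adjusted difference with its 95% CI.
2. Name in advance which indices are log-transformed. PVR is a likely candidate: log it at both times and report a ratio of geometric means. Keep all others on their original scale.
3. State this one form, the 48 h value adjusted for baseline, in the project abstract and in sections 2, 3.1 and 7.1. State separately which form applies to SOFA.

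The cost is wording: no new data, visits or patients. The model spends three degrees of freedom, one for baseline and two for three centres, so the residual df falls from 44 to 41. If r is near zero, simulated power at 0.7 SD is 62–64% for ANCOVA against 63–65% unadjusted, and the CI half-width is 0.60 against 0.59 SD.

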#### **1.4.6 Discussion**

ARDS is often complicated by right ventricular dysfunction (RVD), the incidence of which can be as high as 64%. The pathogenesis includes elevated pulmonary vascular resistance and right ventricular systolic dysfunction [1-3]. The fatality rate of ARDS patients with RVD increased significantly from 30.6% to 56.3%[4,5]. For ARDS patients with right heart failure, currently available drugs include dobutamine and Milrinone, but dobutamine has a high risk of rapid malignant arrhythmia, increases myocardial oxygen consumption, and large doses will increase the proportion of body and lung circulation, leading to systemic hypotension, which is not conducive to the treatment of ARDS patients with right heart failure [14]. Milrinone also has the effect of increasing myocardial contractility, but its application is limited due to systemic hypotension [14]. While levosimendan increases myocardial contractility, it does not increase myocardial oxygen consumption and does not lead to malignant arrhythmias. Many animal experiments have shown that levosimendan can reduce pulmonary circulation resistance, protect myocardium

during myocardial ischemia, improve right ventricular/pulmonary artery coupling, and improve myocardial energy metabolism. Compared with dobutamine and Milrinone commonly used in clinical practice, levosimendan has more advantages and has fewer side effects on patients [14]. Therefore, the purpose of this study is to provide a more powerful research basis for the use of levosimendan in ARDS patients with right heart failure. Because the drug itself has few side effects of arrhythmia and hypotension, and the protocol has fully considered the management of adverse reactions, the risk to subjects will be minimized even if there is no clinical benefit.

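### Section 9(3) uses logistic regression to search for significant predictors in a 58-patient treatment trial, and its example is a recurrence outcome the trial does not have

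*Protocol*

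**What the plan says.** Section 9(3) of the protocol opens with the group comparison, where a CMH chi-square "test considering central effect was used for comparison between groups". It adds chi-square or Fisher tests for categorical measures, and log-rank and Wilcoxon tests for survival. Three modelling sentences follow:

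- On survival: "The Cox risk model was used to analyze the potential influence of covariates (predictors").
- On binary outcomes: "Multivariate logistic regression was used to analyze dichotomous outcomes, such as recurrence rates", with the added statement that "this multivariate model would identify the most significant predictors".
- On adjustment: "Logical or proportional advantage models will be used to adjust for prognostic factors". We read this as logistic or proportional odds models. The factors are not named.

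The endpoints are in section 2: "Primary endpoint: the incidence of RVD after 48h ending of randomization", and among the secondary endpoints "28-day mortality rate, in-hospital mortality rate". The synopsis and section 7.1 give the same binary endpoints. None of the three places lists a recurrence, and none lists the identification of predictors as an endpoint.

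**The concern.** There are two faults in what the text states.

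First, the only binary outcome named in the regression text is foreign to this trial. Neither RVD nor death is named there, so the sentence does not tell the analyst which endpoint the model serves.

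Second, the stated job of the model is to find predictors by their significance. The main objective in section 2 is whether levosimendan improves right heart function, and a search for predictors does not answer that. In a sample this small the search is likely to return noise, which could then be reported as prognostic findings in acute respiratory distress syndrome (ARDS) with RVD. There is also a conditional risk. The next sentence promises adjustment for unnamed prognostic factors, and nothing stops the predictors just selected from filling that role. The adjusted treatment estimate would then come from a model chosen after seeing the outcome.

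**Working it through.** **1. The sample size, reproduced.** Section 3.2 gives a mean difference of 20%, an SD of 20%, two-sided alpha 0.05, power 0.9 and 1:1 allocation. The standardised difference is 20/20 = 1.0. The t-test solution is 22.02 per arm, which rounds up to 23. With 20% dropout, 23/0.8 = 28.75, so 29 per arm and 58 in total. The protocol's figures reproduce: at most 58 patients enter a model, and about 46 if dropout is as planned.

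**2. Chance of a false predictor.** The protocol gives no candidate list, selection rule or threshold. We assume k independent pure-noise candidates tested at 0.05. The chance of at least one false predictor is 1 - 0.95^k:

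| k | 1 - 0.95^k |
|---|---|
| 5 | 22.6% |
| 8 | 33.7% |
| 10 | 40.1% |

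Simulation of a logistic model at n = 58, with treatment forced in and backward elimination at 0.05, agrees: 20-21% for 5 candidates, 31-33% for 8 and 36-42% for 10 across separate runs. A simple univariable screen with 10 candidates gives 40-41%. Ten is not extreme. Section 6 collects echocardiographic indexes, haemodynamics, blood gases, blood counts, liver and kidney function, electrolytes, myocardial enzymes and BNP before dosing.

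**3. Effect on the treatment test.** Simulations used the same n, event rates of 30.6% and 56.3%, and 5 or 10 candidates, either all noise or one truly prognostic. The type I error for treatment was:

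| Analysis | Type I error |
|---|---|
| After backward elimination | 5.0-6.5% |
| All candidates kept in a fixed model | 4.9-7.2% |
| Unadjusted | 4.1-5.4% |

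Selection therefore did little harm to the treatment test in these settings.

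**4. How large a model the deaths would support.** The protocol states no expected number of deaths. Section 1.4.6 gives background rates: "The fatality rate of ARDS patients with RVD increased significantly from 30.6% to 56.3"%. Applying them is our assumption.

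- 58 x 0.306 = 17.7 deaths.
- 58 x 0.563 = 32.7 deaths, leaving 58 - 32.7 = 25.3 survivors.

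A logistic model is limited by the smaller outcome class, so the range is about 18 to 25 of 58. With 46 patients it is 46 x 0.306 = 14.1 to 46 - 46 x 0.563 = 20.1. At 10 patients in the smaller class per parameter (a convention, not in the protocol), 58 patients support about 2 parameters. At 5 per parameter they support about 3 to 5.

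**5. The size of the replacement model.** The synopsis names three centres. Treatment (1), centre (2) and one baseline measure (1) make 4 parameters. For death that is 17.7/4 = 4.4 to 25.3/4 = 6.3 patients per parameter. For RVD at 48 h the protocol gives no expected rate; the smaller class cannot exceed 58/2 = 29, so the most favourable figure is 29/4 = 7.25. Four parameters is already the upper end, which is why the mortality model should be no larger.

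**The case against.** The strongest defence is that the treatment comparison does not rest on this model. The CMH, chi-square or Fisher, and log-rank tests need no fitted set of predictors. That stands.

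A reader might infer that the plan offers predictor selection in place of an adjusted treatment effect. The documents do not support this. The very next sentence plans adjustment for prognostic factors, and nowhere is it said that the selected predictors become the adjustment set. The link is possible, not stated.

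A reader might also infer that the treatment confidence interval would be too narrow. The simulated type I error near 5-6.5% does not show that.

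Nor is the absence of a named baseline severity covariate a fault in itself. Covariate lists are commonly left to a statistical analysis plan, and this trial's plan is not shown.

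It can further be said that backward elimination is our choice, and that the sentence could simply mean reporting which terms in a fitted model are significant. That is fair, but it does not remove the problem. With all-noise candidates kept in a fixed full model, at least one was falsely significant in 23-48% of runs, against 21-42% after elimination. The source is multiplicity, and it arises under either reading.

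Finally, the death counts rest on background rates that section 1.1.1 presents with COVID-19 ARDS. The lower rate may describe patients without RVD, whereas every enrolled patient has it. The counts serve only to indicate model size.

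What the defence does not answer is the stated text. A later analysis plan that follows it inherits the wrong outcome and the predictor search, and one that drops them departs from the protocol.

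**Conclusion.** The point holds as a fault in the regression text of section 9(3), not in the primary comparison. The example outcome does not belong to this trial, and the stated purpose of the model does not serve the trial's objective. Assuming 5 to 10 noise candidates tested at 0.05, about 20-40% of such trials would report at least one false predictor. A data-dependent adjusted estimate is a risk only if the selected predictors are reused as the prognostic factors. The limiting class of about 18-25 for mortality depends on applying the quoted background rates to all 58 patients. The correction should be made, but it is one of wording and of secondary modelling.

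**What to change.** Amend section 9(3) as follows.

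- Delete the recurrence example and name the binary outcomes: RVD at 48 h, 28-day death and in-hospital death.
- Replace the predictor-identification sentence with one prespecified logistic model for RVD at 48 h containing treatment, centre and one pre-dose right heart measure, for example RV FAC. Section 6 already collects these measures before dosing. Report the treatment odds ratio with its 95% CI, and use no significance-based selection.
- State that these prespecified terms are the prognostic factors of the adjustment sentence, and that the centre-stratified CMH comparison stays as it is.
- For 28-day death, use a model of the same size or smaller, for example treatment and one baseline measure. With 2 parameters that is 17.7/2 = 8.9 to 25.3/2 = 12.7 patients in the smaller class per parameter.
- Label any search for predictors, including one by the Cox model, as hypothesis-generating.

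The cost is a few sentences, with no new data and no change in sample size. The choice of baseline measure has to be made and recorded before the outcome data are seen. The downside is that the main report can make no confirmatory claim about predictors.
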